### 7.4.2 Non-hematological Adverse Events

For all instances of **mucositis** occurring on the planned dosing day, treatment modifications will be made as outlined in Table 7.2. For **treatment-related cardiovascular, dermatological, hepatic, neurologic, renal, or respiratory** AEs, treatment modifications will be made as outlined in Table 7.3. For all other non-hematological treatment-related AEs, treatment modifications should be made at the investigator’s discretion.

**Table 7.2. Pralatrexate Treatment Modifications for Mucositis**

Mucositis Grade on Planned Dosing Day	Action
0 or 1	
 
No change in pralatrexate dose.
 

2	
 
Omit this week's dose of pralatrexate. Administer with no change in pralatrexate dose if resolution to Grade 0-1.
 
If reoccurrence, omit this week's dose, upon resolution to Grade 0-1, reduce the dose to next lower dose level.
 

3	
Do not administer pralatrexate until recovery to Grade 0-1.
 
 
Upon recovery to Grade 0-1, reduce to next lower dose level
 
Discontinue pralatrexate if <math>\geq</math> Grade 3 mucositis persists for <math>\geq 2</math> consecutive weeks or reoccurs within 28 days if on <math>10 \text{ mg/m}^2</math>
 

4	
 
Discontinue pralatrexate.
 

**Table 7.3. Pralatrexate Treatment Modifications for Treatment-related Cardiovascular, Dermatological, Hepatic, Neurologic, Renal, or Respiratory AEs**

Event Grade	Action
0-2	
 
No change in pralatrexate dose.
 

3	
Do not administer pralatrexate until recovery to <math>\leq</math> Grade 2.
 
 
Upon recovery to <math>\leq</math> Grade 2 administer pralatrexate without a change in dose.
 
If the patient experiences the same Grade 3 treatment-related AE do not administer until recovery to <math>\leq</math> Grade 2 and administer with a reduction to the next lower dose level.
 
Discontinue pralatrexate if the same Grade 3 treatment-related AE recurs within 28 days at <math>10 \text{ mg/m}^2</math>.
 

4	
 
Discontinue pralatrexate.
 

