**Table 7.1. Pralatrexate Treatment Modifications for Hematological AEs**

Hematological Parameter on Planned Dosing Day	Action
ANC $\geq$ 1000/ $\mu$ L ( $\leq$ Grade 2) or platelets $\geq$ 50,000/ $\mu$ L ( $\leq$ Grade 2)	
 
No change in pralatrexate dose.
 

ANC $\geq$ 500/ $\mu$ L and $<$ 1,000/ $\mu$ L (Grade 3) without fever	
 
Administer cytokine prophylaxis and/or treatment per ASCO guidelines.
 
Do not administer pralatrexate until recovery to <math>\leq</math> Grade 2 (<math>\geq</math> 1000/<math>\mu</math>L). Upon recovery to <math>\leq</math> Grade 2, administer pralatrexate without a change in dose.
 

ANC $\geq$ 500/ $\mu$ L and $<$ 1,000/ $\mu$ L (Grade 3) associated with single oral temperature $\geq$ 38.1°C requiring parenteral antibiotics or ANC $<$ 500/ $\mu$ L (Grade 4)	
 
Administer cytokine prophylaxis and/or treatment per ASCO guidelines.
 
Do not administer pralatrexate until recovery to <math>\leq</math> Grade 2 (<math>\geq</math> 1000/<math>\mu</math>L). Upon recovery to <math>\leq</math> Grade 2, administer pralatrexate without a change in dose.
 
If reoccurrence within 28 days, reduce the pralatrexate dose to the next lower dose level.
 
Discontinue pralatrexate if event reoccurs at 10 mg/m^2 despite cytokine support.
 

Platelets $<$ 50,000/ $\mu$ L ( $\geq$ Grade 3)	
 
Do not administer pralatrexate until recovery to <math>\leq</math> Grade 2 (<math>\geq</math> 50,000/<math>\mu</math>L). Upon recovery to <math>\leq</math> Grade 2, administer pralatrexate without a change in dose.
 
If a platelet count of Grade 4 (<math><</math> 25,000/<math>\mu</math>L) reoccurs within 28 days, reduce the pralatrexate dose to the next lower dose level.
 
Discontinue pralatrexate if a platelet count of Grade 4 (<math><</math> 25,000/<math>\mu</math>L) occurs twice within 28 days at 10 mg/m^2.
 

ANC – absolute neutrophil count

°C – degrees Celsius

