### 11.1 Criteria for Study Treatment Discontinuation

Patients will receive study treatment (pralatrexate or observation) until one of the following criteria for study treatment discontinuation applies:

- Development of PD
- Initiation of RT or systemic chemo/biological therapy for treatment of PTCL
- Receipt of systemic steroids > 10 days, with the exception of those as stated in exclusion criterion #5 (see [Section 8.4](#))
- Development of an AE that interferes with the patient's participation
- Lost to follow-up
- Patient decision
- Investigator decision
- Sponsor decision

In addition, for those patients randomized to the Pralatrexate Arm, additional pralatrexate treatment discontinuation criteria are:

- 3 or more consecutive doses of pralatrexate omitted or more than 28 days between doses of pralatrexate
- Treatment with pralatrexate for 2 years

Patients will be seen for the Initial Follow-up Visits as outlined in [Section 10.7](#).

If an investigator feels that a patient would continue to benefit from pralatrexate therapy after completion of 2 years' therapy, they should discuss with the sponsor's medical contact and agree whether or not it is appropriate to continue treatment.

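### The mandatory stop for Grade 4 mucositis is tied to the grade on the planned dosing day, so an episode that settles before the next dose falls in the row that leaves the dose unchanged

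*Protocol*

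**What the plan says.** Protocol Section 7.4.2 states that for mucositis "occurring on the planned dosing day, treatment modifications will be made as outlined in Table 7.2". The table's own column heading repeats the limit: "Mucositis Grade on Planned Dosing Day". The rows are:

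- Grade 0 or 1: dose unchanged.
- Grade 2: omit that week's dose, then "Administer with no change in pralatrexate dose if resolution to Grade 0-1"; on reoccurrence, go down one level after recovery.
- Grade 3: hold, then "Upon recovery to Grade 0-1, reduce to next lower dose level". This row also stops the drug if mucositis of Grade 3 or higher lasts 2 or more consecutive weeks, or reoccurs within 28 days at 10 mg/m2.
- Grade 4: permanent discontinuation.

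Section 4.3.1 (Precautions) has a wider trigger. Mucositis of Grade 2 or higher that is observed, with no mention of the dosing day, leads to modification under Table 7.2.

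Table 7.3 works from the grade of the event with no dosing-day limit, and stops the drug at Grade 4. Its organ systems are cardiovascular, dermatological, hepatic, neurologic, renal and respiratory; mucositis is not among them. Anything outside the tables is left to judgement: "For all other non-hematological treatment-related AEs, treatment modifications should be made at the" investigator's discretion.

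The SAP summarises dose modifications but contains no dosing rule.

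**The concern.** The sponsor did not leave Grade 4 mucositis to judgement; it wrote a mandatory stop. As worded, that stop depends on whether Grade 4 is still present at a dosing visit, not on whether it occurred. Of two patients with the same Grade 4 episode, one with the episode on a dosing day comes off the drug for good, while the other, whose episode rose and cleared between doses, falls in the row that continues the same dose.

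What is at stake is patient safety and uniform handling across sites. These patients have responded to CHOP, are compared with observation, and may receive pralatrexate for up to 2 years. Mucositis is a named precaution for the drug in Section 4.3.1. A rule that sites can read in two ways will also be applied in two ways.

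**Working it through.** The plan gives no figure to reproduce. The check is a reading of the text plus the dosing calendar.

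**Length of the gaps.** The inputs are three weekly doses in a 4-week cycle (Section 7.2) and a window of 1 day either side at each dose (Synopsis, Treatment Plan). Doses fall on days 1, 8 and 15, and the next cycle starts on day 29.

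- Within a cycle: 8 − 1 = 7 days.
- Across the rest week: 29 − 15 = 14 days. With the windows, the shortest gap is (29 − 1) − (15 + 1) = 12 days and the longest is (29 + 1) − (15 − 1) = 16 days.

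**What Table 7.2 requires after a Grade 4 peak between doses**, by the grade found on the dosing day:

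- Grade 0-1: same dose, that day.
- Grade 2: omit one dose, then the same dose (one level lower if this is a reoccurrence).
- Grade 3: hold, then one level lower; stop if the 2-week rule, or the 28-day rule at 10 mg/m2, is met.
- Grade 4: stop.

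Only the last is a stop on grade alone.

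**Whether the 2-week rule closes the gap.** It cannot act on an episode that starts and settles within a 7-day interval. Across the rest week the interval is 12 to 16 days, so an episode would need to stay at Grade 3 or higher for nearly all of it. The rule therefore catches prolonged episodes, not a short one that has reached Grade 0-1 by day 29.

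**Whether another section requires the stop.**

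- Section 4.3.1 has the wider trigger but supplies no action of its own. It sends the reader to a table whose heading restores the dosing-day limit.
- Table 7.3 would require the stop, but does not cover mucositis.
- The pre-dose check in 10.4.2 and 10.4.3 is in the present tense: it asks whether the patient is now experiencing an adverse event that warrants a change. A resolved episode passes it.
- Section 13.3 asks for symptom assessment before each dose, and Appendix 1 lists no rest-week safety visit.
- Section 11.1 allows a stop for "Development of an AE that interferes with the" patient's participation, or by investigator decision. Neither is tied to a grade.

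**Comparison with blood counts.** Table 7.1 uses the same basis, "Hematological Parameter on Planned Dosing Day". There a first Grade 4 neutrophil count leads, after recovery, to the same dose; the consequence comes later: "If reoccurrence within 28 days, reduce the pralatrexate dose to the next lower dose level". Missing a transient low count therefore costs only a possible later reduction. For mucositis, the same convention separates a permanent stop from unchanged treatment.

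**The case against.** The strongest reply is that the protocol is not silent. Section 4.3.1 can fairly be read as sending any observed Grade 4 mucositis to the Grade 4 row. The bone-marrow paragraph of the same section limits itself to counts before each dose, while the mucositis paragraph does not, so the broader wording may be meant. This stands in part: the defect is an inconsistency between 4.3.1 and 7.4.2 with Table 7.2, not the plain absence of any rule. But a site that follows the table as headed would continue the dose, and the inconsistency is itself a reason to amend.

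It is also true that investigators can stop treatment on their own judgement, that adverse events are reviewed at each dose visit after the first, and that an event meeting the serious criteria reaches the sponsor within 24 hours and is assessed by a medical monitor. These safeguards are real. None sets the dosing action that the Grade 4 row sets.

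A reader might go further and infer that a Grade 3 episode which clears between doses is likewise mishandled, since no reduction follows. The documents do not support calling that an error. Section 5 explains that a break after three doses may help patients tolerate full-dose treatment over time, and Table 7.1 shares the dosing-day convention. Resuming the same dose after recovery in the rest week may be what was intended.

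**Conclusion.** The point holds for Grade 4 mucositis. Under Section 7.4.2 and Table 7.2 as written, a Grade 4 episode that settles to Grade 0-1 before the next dose carries no mandatory stop. Section 4.3.1 points the other way without resolving the matter. Exceptions are mucositis of Grade 3 or higher lasting at least 2 consecutive weeks, or recurring within 28 days at 10 mg/m2.

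The size cannot be given as a number of patients, because the documents report no mucositis rate. The 14-day gap is half of a 28-day cycle (14/28), but that is a share of the calendar and should not be read as a risk: an episode must both reach Grade 4 and settle within one gap to escape the rule. Nor should a reader infer a threat to the efficacy analysis; the primary PFS and OS tests are not directly affected.

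The conclusion assumes that sites follow the table heading and the sentence that invokes it in preference to the looser wording in 4.3.1. It is a modest safety clarification that is cheap to make.

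**What to change.** 1. In Table 7.2, change the Grade 4 row to: Grade 4 on the planned dosing day or at any time since the previous dose: discontinue pralatrexate.
2. Amend the first sentence of 7.4.2 to match, so that it and 4.3.1 agree on Grade 4. State there that Grades 2 and 3 continue to be handled by the dosing-day grade.
3. In the existing adverse-event step of 10.4.2 and 10.4.3, record the worst mucositis grade since the previous dose.

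Leave the Grade 2 and Grade 3 rows, the holds until Grade 0-1, and the 2-week and 28-day rules as they are.

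The cost is one table row, one amended sentence with its clarification, a phrase in each of two procedure lists, and a notice to sites. No visit or test is added. The downsides are a few more discontinuations and some grades reconstructed from the patient's account at the next visit, since no safety visit is scheduled in the rest week.

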### 7.2 Pralatrexate Administration

One cycle of pralatrexate therapy is 4 weeks in duration and consists of 3 weekly doses of pralatrexate IV push over 30 seconds and up to 5 minutes, with 1 week of rest. The initial dose of pralatrexate will be 30 mg/m^2/week. For patients with a body surface area (BSA) > 2 m^2, the administered dose will be calculated using a capped BSA value of 2 m^2. Pralatrexate dose reduction to 20 mg/m^2 with further reduction to 15 and 10 mg/m^2 will be allowed for defined toxicities (see [Section 7.4](#)). Pralatrexate will continue to be administered until a criterion for study treatment discontinuation is met ([Section 7.3](#)) or up to a maximum of 2 years.

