## 7.4 Treatment Modifications of Pralatrexate

Pralatrexate dose modifications will be allowed according to the criteria outlined below in [Table 7.1](#), [Table 7.2](#), and [Table 7.3](#). Dose reduction to 20 mg/m^2 with further reductions to 15 mg/m^2 and 10 mg/m^2 will be allowed for the toxicities defined in the tables below. If an AE occurs that prevents the administration of pralatrexate on the scheduled dosing day ( $\pm$  1 day), the dose will be omitted that week and the patient will be reassessed the following week to proceed to the next dose of the cycle.

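### Tables 7.2 and 7.3 order a dose reduction in four situations that can arise at 10 mg/m², the lowest listed level, and give no action that can be carried out there

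*Protocol*

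**What the plan says.** Protocol section 7.2 sets the start: "The initial dose of pralatrexate will be 30 mg/m 2 /week". Section 7.4 gives the first reduction as 20 mg/m², "with further reductions to 15 mg/m 2 and 10 mg/m 2 will be allowed for the toxicities defined in the tables below". No level below 10 mg/m² appears in the synopsis, in sections 7.2 or 7.4, or in SAP section 3.

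The reduction instructions for non-hematological events are:

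- Table 7.2, Grade 2 mucositis: on recurrence, skip that week's dose and, "upon resolution to Grade 0-1, reduce the dose to next lower dose level". The row has no time window and does not mention 10 mg/m².
- Table 7.2, Grade 3 mucositis: "Upon recovery to Grade 0-1, reduce to next lower dose level". A separate bullet stops treatment if the event lasts 2 consecutive weeks or longer, or comes back within 28 days in a patient on 10 mg/m².
- Table 7.3, the same Grade 3 treatment-related event again: hold until recovery, then "administer with a reduction to the next lower dose level". A separate bullet stops treatment if it recurs within 28 days at 10 mg/m².
- Grade 4 in either table: stop, at any dose.

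Table 7.1 is built differently. Its reductions are triggered only by recurrence within 28 days, and each has a counterpart at the lowest level. The neutrophil row reads "Discontinue pralatrexate if event reoccurs at 10 mg/m"² and adds the condition that cytokine support has been given. The platelet row stops after two Grade 4 counts within 28 days at 10 mg/m².

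**The concern.** A dose-modification table has to give an action at every dose a patient can be on. In Table 7.1 the reduction trigger and the stop at 10 mg/m² fit together. In the Grade 3 rows of Tables 7.2 and 7.3 they do not: the reduction has no time limit, while the recurrence stop is limited to 28 days. In the Grade 2 row there is a reduction and no stop at all. What falls between the two is an instruction to move to a level that the protocol does not contain.

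The first stake is patient safety. Protocol section 4.3.1 names mucositis of Grade 2 or higher as a reason to modify the dose under Table 7.2. A site holding a patient at 10 mg/m² with recurrent mucositis is sent to that table and finds no step it can take. The second stake is the reporting of treatment in the pralatrexate arm. SAP section 8.6 tabulates cumulative dose, dose modifications with reasons, and adverse events leading to reduction or discontinuation. If sites resolve the gap in different ways, part of what those tables show will be local interpretation.

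**Working it through.** This is a check of a decision rule. The plan states no figure on this point to reproduce, and no sample size, power or alpha figure enters.

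**Inputs.** Levels 30 > 20 > 15 > 10 mg/m² (Protocol 7.2 and 7.4), and the reduction and stop rules of Tables 7.1 to 7.3.

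**Method.** Take each situation in which a table orders a reduction or a related stop, apply it at each level, and record whether the result is a listed lower dose, an explicit stop, or nothing that can be carried out.

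| Situation | At 30, 20 or 15 mg/m² | At 10 mg/m² |
|---|---|---|
| 7.1 neutrophils: febrile Grade 3, or Grade 4, recurring within 28 days | one level down | stop if it recurs despite cytokine support |
| 7.1 platelets: Grade 4 recurring within 28 days | one level down | stop |
| 7.2 Grade 2 mucositis, recurrence at any interval | one level down | **no executable action** |
| 7.2 Grade 3 mucositis, first event, under 2 weeks | one level down | **no executable action** |
| 7.2 Grade 3 mucositis, 2 weeks or longer | wording open (see below) | stop |
| 7.2 Grade 3 mucositis, recurring within 28 days | one level down | stop |
| 7.2 Grade 3 mucositis, recurring after 28 days, under 2 weeks | one level down | **no executable action** |
| 7.3 same Grade 3 event, recurring within 28 days | one level down | stop |
| 7.3 same Grade 3 event, recurring after 28 days | one level down | **no executable action** |

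Above 10 mg/m² every ordered reduction leads to a listed dose. At 10 mg/m² four situations have no executable action: three in Table 7.2 and one in Table 7.3. The wording open in the fifth row is whether the 10 mg/m² condition in the Grade 3 stop applies to persistence as well as to recurrence. At 10 mg/m² the answer is a stop on either reading.

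**Can a patient be at 10 mg/m² and meet one of these?** Yes. The three tables draw on the same dose levels, so earlier reductions may come from another toxicity or grade. Section 7.4 describes no return to a higher dose. Treatment may last 2 years, which is 104 / 4 = 26 cycles, so a recurrence after more than 28 days is possible.

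**Does another provision supply the missing action?**

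- Investigator discretion in section 7.4.2 is reserved for non-hematological events outside Tables 7.2 and 7.3.
- The criterion in sections 7.3 and 11.1 on three missed doses in a row, or a gap exceeding 28 days, does not reach an event that settles after one or two omissions.
- The other criteria in those sections, the investigator's decision and an adverse event that gets in the way of participation, permit stopping. They do not say what follows when a table orders a reduction that is not available.

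**The case against.** The strongest reply is that the protocol already limits what a site may do. Reductions below 10 mg/m² are not among those section 7.4 allows, section 16.3 holds investigators to the protocol, and sections 7.3 and 11.1 let the investigator stop any patient. Both Grade 3 rows carry an explicit stop at 10 mg/m², and Grade 4 ends treatment at any dose. What is left is a small set of situations at the bottom of the scale, affecting descriptive tables only.

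Most of this stands, and it rules out several stronger readings. A reader might infer that Tables 7.2 and 7.3 ignore the lowest level. They do not: they state stops there, but with a narrower reach than the reductions they accompany. A reader might infer that nothing in the text would support stopping. The general criteria do support it. A reader might infer that sites are bound to act differently. The documents show only that they may.

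The reply does not close the gap, because permission to stop is not an instruction for the floor case. Nor is it safe to read the absence of a lower level as a stop. Applied to every row, that reading would leave the 28-day limits on the Grade 3 stops with nothing to do. Applied to the Grade 2 row alone, it would make recurrent Grade 2 mucositis stricter than a Grade 3 recurrence after 28 days.

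**Conclusion.** The point holds in a limited form. Four situations at 10 mg/m² carry a reduction instruction that cannot be executed, and recurrent Grade 2 mucositis is the clearest because its row has neither a time window nor a stop. This is an incomplete instruction that conflicts with the protocol's own list of levels, not a disputed design choice.

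How many patients it touches cannot be derived. A reader might apply an assumed percentage to the 366 patients planned for the pralatrexate arm. The documents offer no basis for one, and it would count patients who reach 10 mg/m², not the equal or smaller group who then have one of the four events. The PDX-008 figure in Protocol section 5 (24 of 57, or 42%, needing a modification at doses 4 to 6) comes from a different schedule and does not show how many reach the lowest level.

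A reader might also infer that the efficacy comparison is compromised. It is not: PFS and OS are tested in all randomized patients as assigned, whatever treatment they received (Protocol 15.3.1, SAP 6.1), so the validity of those tests and the sample size are unaffected. The consequence lies in patient safety at the lowest dose and in how far the pralatrexate-arm exposure, modification and discontinuation summaries can be interpreted. It should be corrected because it concerns toxicity management and costs little. The conclusion assumes that the published levels are complete and that the Study Instructions, which are not available here, do not cover the case.

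**What to change.** Reconcile the reduction and stop instructions in Tables 7.2 and 7.3 with the dose levels in section 7.4 and with the structure of Table 7.1, so that every row has an action that can be carried out at the lowest listed level. The rows to settle are recurrent Grade 2 mucositis, Grade 3 mucositis (a first event under 2 weeks, and recurrence after 28 days), and the same Grade 3 event under Table 7.3 recurring after 28 days. In the same edit, make clear whether the 10 mg/m² condition in the Grade 3 mucositis stop applies to persistence as well as to recurrence. What the action should be is for the sponsor's medical team; no rule is proposed here.

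The cost is a short protocol clarification or amendment, about one line per affected row. Sample size, alpha and the planned analyses do not change.

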## 8 PATIENT POPULATION

### 8.1 Number of Patients and Patient Selection

The target patient population is adult patients with previously undiagnosed PTCL who have achieved an objective response after pre-study first-line treatment with at least 6 cycles of one of the following CHOP-based treatments:

- a. CHOP 21
- b. CHOP 14
- c. CHOEP
- d. Other CHOP variants

A total of 549 patients will be randomized 2:1 to pralatrexate or observation.

